8.5.1.2. Analysis of Primary Efficacy Endpoint

The null hypothesis is that the proportion of subjects achieving HIV-1 RNA $<$ 50 copies/mL (as defined by the US FDA-defined snapshot algorithm) at Week 48 in B/F/TAF is at least 12% lower than the response rate in DTG + F/TDF; the alternative hypothesis is that the response rate in B/F/TAF is less than 12% lower than that in DTG + F/TDF.

Non-inferiority will be assessed using the conventional confidence interval approach. The point estimate of treatment difference (B/F/TAF – DTG+F/TDF) and the associated 2-sided 95% confidence interval will be constructed using a normal approximation method based on stratified Mantel-Haenszel proportions, where stratification factor include baseline HIV-1 RNA (\leq 100,000 copies/mL vs. $>$ 100,000 copies/mL).

It will be concluded that B/F/TAF is non-inferior to DTG + F/TDF if the lower bound of the 2-sided 95% CI of the difference (B/F/TAF – DTG+F/TDF) in the response rate is greater than -12%.

If non-inferiority of B/F/TAF to DTG+F/TDF is established, the lower bound of the 95% CI will be compared to 0; if the lower bound of the 95% CI is greater than 0, then superiority of B/F/TAF to DTG+F/TDF will be established.

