8.5.1.3. Analysis of Co-Primary Efficacy Endpoint for HBV

The null hypothesis is that the proportion of subjects with plasma HBV DNA < 29 IU/mL at Week 48 as determined by Missing=Failure approach in B/F/TAF is at least 12% lower than the response rate in DTG + F/TDF; the alternative hypothesis is that the response rate in B/F/TAF is less than 12% lower than that in DTG + F/TDF. For Missing = Failure approach, all missing data will be treated as HBV DNA \geq 29 IU/mL.

Non-inferiority will be assessed similarly as for the primary efficacy endpoint, except the stratification factors include HBeAg status (positive vs. negative) and baseline HBV DNA (< 8 log₁₀ IU/mL vs. \geq 8 log₁₀ IU/mL). To control type I error for the assessment of the primary and the co-primary efficacy endpoints, the hypothesis testing will be performed using the fallback procedure {[Wiens 2005](#)} in the sequential order with pre-specified 1-sided alpha level. The primary hypothesis of non-inferiority of B/F/TAF relative to DTG + F/TDF, with respect to the proportion of subjects with HIV-1 RNA < 50 copies/mL at Week 48 (as defined by the FDA snapshot analysis) will be tested first. Non-inferiority test will be performed at one-sided, 0.025 alpha level. If non-inferiority is established, the co-primary hypothesis of non-inferiority of B/F/TAF relative to DTG + F/TDF, with respect to the proportion of subjects with plasma HBV DNA < 29 IU/mL at Week 48 will be tested second at one-sided, 0.025 alpha level. Otherwise, the co-primary endpoint will not be tested at all.

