2.2. Interim Analyses

2.2.1. Week 48 Analysis

The Week 48 analysis was conducted after all participants either completed their Week 48 visit or prematurely discontinue from the study drug.

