6. EFFICACY ANALYSES

All necessary summaries on the primary efficacy endpoint (at Week 48) and the secondary endpoints at Weeks 48 and 96 have been performed as part of the Week 48 CSR and Week 96 CSR, and will not be repeated for the final analysis.

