6.1. Primary Efficacy Endpoints

6.1.1. Definition of the Primary Efficacy Endpoints

The primary efficacy endpoint is the proportion of participants with HIV-1 RNA < 50 copies/mL at Week 48 as determined by the US FDA-defined snapshot algorithm {U. S. Department of Health and Human Services 2015}. The proportions are expressed as percentages for presentation purposes.

The co-primary efficacy endpoint is the proportion of participants with plasma HBV DNA < 29 IU/mL at Week 48 as defined by Missing = Failure (M = F) approach.

The statistical analysis methods for the primary and co-primary efficacy endpoints were described in the Week 48 SAP and the analyses were performed in the Week 48 analysis, and will not be repeated for the final analysis.

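### Once HIV non-inferiority passes, the protocol opens both HIV superiority and HBV non-inferiority at the full one-sided 0.025, with no order or alpha split between them

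*Protocol*

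**What the plan says.** Protocol section 8.5.1.2 sets the HIV non-inferiority test on the two-sided 95% confidence interval with a 12-point margin. If that test passes, the same lower bound is compared with zero, and "if the lower bound of the 95% CI is greater than 0, then superiority of B/F/TAF to DTG+F/TDF will be established". HIV non-inferiority is the only condition placed on this step. No alpha is stated for it, but a two-sided 95% interval implies one-sided 0.025.

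Section 8.5.1.3 introduces its testing sequence with the words "To control type I error for the assessment of the primary and the co-primary efficacy endpoints". For HIV, "Non-inferiority test will be performed at one-sided, 0.025 alpha level". Then: "If non-inferiority is established, the co-primary hypothesis of non-inferiority of B/F/TAF relative to DTG + F/TDF" "will be tested second at one-sided, 0.025 alpha level". The synopsis gives the same sequence. Neither place mentions HIV superiority.

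SAP section 3.5 confines alpha adjustment to the Week 48 primary endpoints and does not mention superiority. SAP section 6.1.1 adds: "The statistical analysis methods for the primary and co-primary efficacy endpoints were described in the Week 48 SAP". That document was not available for this review; the SAP at hand covers the final analysis only.

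**The concern.** One passed test opens two further tests, each at the full one-sided 0.025. Moving from non-inferiority to superiority on a single endpoint costs no alpha, and testing HIV non-inferiority then HBV non-inferiority is sound. The two arrangements do not combine freely: the alpha released by HIV non-inferiority is used once for HIV superiority and again for HBV non-inferiority. A fixed sequence needs one successor at each step, or a division of alpha between successors, and the protocol text gives neither.

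As written, a positive Week 48 HIV superiority result could be presented as confirmatory beside the HBV non-inferiority claim, although the joint error rate exceeds the level that section 8.5.1.3 sets out to control.

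**Working it through.** **Inputs.** From protocol section 8.8: 120 per arm, a 12-point margin, one-sided 0.025, 91% HIV response and 88% HBV response in both arms. The documents give no correlation between the endpoints, so correlations of 0 to 0.7 are assumed. The IDMC penalty of 0.00001 (section 8.9) is too small to matter here.

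**The plan's own figures.** Power = Φ(0.12/√(2p(1−p)/120) − 1.96).
- HIV, p = 0.91: SE = √(2×0.91×0.09/120) = 0.0369; 0.12/0.0369 = 3.25; power 90.1% (stated 90%).
- HBV, p = 0.88: SE = √(2×0.88×0.12/120) = 0.0420; power 81.6% (stated 81%).

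Both reproduce.

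**Error rate where both follow-on nulls are true.** Take HIV equal at 91/91, so that non-inferiority is true and superiority false, and HBV at the margin, 76 against 88. Let Z1 and Z2 be the standardised HIV and HBV statistics, z = 1.96 and d = 3.25.
- As written: P(Z1 > z) + P(z−d < Z1 ≤ z, Z2 > z). With independence, 0.025 + (0.9011 − 0.025)×0.025 = 0.0469.
- Superiority only after HBV non-inferiority: P(Z1 > z−d, Z2 > z) = 0.9011×0.025 = 0.0225.

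| Assumed correlation | As written | Ordered |
|---|---|---|
| 0 | 4.69% | 2.25% |
| 0.3 | 4.72% | 2.45% |
| 0.5 | 4.53% | 2.49% |
| 0.7 | 4.17% | 2.50% |

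**Exact binomial check** (unstratified Wald interval, independent endpoints). The single tests have exact sizes of 2.70% (HIV superiority) and 2.65% (HBV non-inferiority), and HIV non-inferiority passes with probability 0.9024. As written: 0.0270 + (0.9024 − 0.0270)×0.0265 = 0.0502. Ordered: 0.9024×0.0265 = 0.0239. Part of the 5.0% is therefore small-sample error of the Wald interval.

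**How quickly the excess fades** (normal approximation, as written).

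| True rates, B/F/TAF vs control | Independent | Correlation 0.3 to 0.7 |
|---|---|---|
| HIV 90 vs 91, HBV at margin | 3.34% | 3.27–3.56% |
| HIV 89 vs 91, HBV at margin | 2.48% | 2.83–2.94% |
| HIV equal, HBV 75 vs 88 | 3.84% | 3.43–3.84% |
| HIV equal, HBV 74 vs 88 | 3.30% | 2.99–3.29% |
| HIV equal, HBV 73 vs 88 | 2.96% | 2.75–2.95% |

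At the planned 91/91 and 88/88, HIV superiority is the only false hypothesis open, so the error stays at 2.5%.

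**How hard superiority is to reach.** With 109/120 (90.8%) on control, the unstratified Wald lower bound is −0.2 points at 116/120 and first exceeds zero at 117/120 (97.5%), where it is +0.8 points.

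The planned stratified Mantel-Haenszel interval was not computed, because stratum sizes and rates are not given.

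**The case against.** The strongest objection is that the governing text may lie elsewhere. The SAP refers the primary and co-primary methods to the Week 48 SAP, which may set the order. This stands, and it limits the finding to the protocol text.

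Second, superiority has little standing as a planned hypothesis. The formal null and alternative are non-inferiority only, no objective names superiority, the synopsis omits it, and the sample size section gives it no power. It could be read as a supplementary look at the same interval. Against that, section 8.5.1.2 says superiority will be established, which is confirmatory wording, and nothing in the protocol or the SAP at hand calls the comparison descriptive.

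Third, the phrase about testing HBV second might be taken to put HIV superiority third. It orders HBV after HIV non-inferiority only; section 8.5.1.2 makes superiority depend on HIV non-inferiority alone.

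Fourth, 4.7% is a corner case. That is true, as the second table shows, although strong error control is judged at such boundary points, and HIV equality is the plan's own assumption.

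Fifth, an order added now would be post hoc. This also stands and shapes the remedy.

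**Conclusion.** The gap is real in the protocol text and should be fixed. HIV superiority and HBV non-inferiority both open at one-sided 0.025 on the same trigger. With HIV equal at 91% and HBV at the margin, the chance of at least one false claim is 4.2% to 4.7% for assumed correlations of 0, 0.3, 0.5 and 0.7, against 2.3% to 2.5% if superiority comes last. These are normal approximations with unstratified standard errors. The excess is smaller elsewhere and absent at the planned rates.

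Only a confirmatory HIV superiority claim is affected. Confidence is medium, because the Week 48 SAP may already have set the order.

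**What to change.** Add one sentence to protocol section 8.5.1.2, stating either that HIV superiority is tested only after HBV non-inferiority is established, or that the comparison with zero is descriptive and outside type I error control.

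Timing decides what can still be done. The SAP records that "The Week 48 analysis was conducted after all participants either completed their Week 48 visit" or stopped study drug early, and that the primary and secondary summaries "have been performed as part of the Week 48 CSR and Week 96 CSR, and will not be repeated for the final analysis". A new order would therefore be post hoc. Later reporting should call any HIV superiority result descriptive, unless the Week 48 SAP had fixed its place before unblinding.

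**Cost.** Neither option changes a non-inferiority test.
- *Superiority last:* it also needs HBV non-inferiority to pass (about 82% power at 88/88), so with independent endpoints about 18% of superiority results would be withheld. Superiority power falls from 23% to 19% at an assumed 95 against 91, and from 51% to 41% at an assumed 97 against 91.
- *Descriptive label:* no power is lost, but the confirmatory superiority claim is given up.

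Splitting alpha as 0.0125 and 0.0125 would also control the error, but HBV non-inferiority power would drop from 81.6% to 73.2%, so it is not recommended.

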8.5.1.3. Analysis of Co-Primary Efficacy Endpoint for HBV

The null hypothesis is that the proportion of subjects with plasma HBV DNA < 29 IU/mL at Week 48 as determined by Missing=Failure approach in B/F/TAF is at least 12% lower than the response rate in DTG + F/TDF; the alternative hypothesis is that the response rate in B/F/TAF is less than 12% lower than that in DTG + F/TDF. For Missing = Failure approach, all missing data will be treated as HBV DNA \geq 29 IU/mL.

Non-inferiority will be assessed similarly as for the primary efficacy endpoint, except the stratification factors include HBeAg status (positive vs. negative) and baseline HBV DNA (< 8 log₁₀ IU/mL vs. \geq 8 log₁₀ IU/mL). To control type I error for the assessment of the primary and the co-primary efficacy endpoints, the hypothesis testing will be performed using the fallback procedure {[Wiens 2005](#)} in the sequential order with pre-specified 1-sided alpha level. The primary hypothesis of non-inferiority of B/F/TAF relative to DTG + F/TDF, with respect to the proportion of subjects with HIV-1 RNA < 50 copies/mL at Week 48 (as defined by the FDA snapshot analysis) will be tested first. Non-inferiority test will be performed at one-sided, 0.025 alpha level. If non-inferiority is established, the co-primary hypothesis of non-inferiority of B/F/TAF relative to DTG + F/TDF, with respect to the proportion of subjects with plasma HBV DNA < 29 IU/mL at Week 48 will be tested second at one-sided, 0.025 alpha level. Otherwise, the co-primary endpoint will not be tested at all.

8.5.2. Secondary Analyses

8.5.2.1. Secondary anti-HIV Efficacy Analysis

The proportion of subjects who achieve HIV-1 RNA < 50 copies/mL at Week 96 as defined by the US FDA-defined snapshot algorithm, will be analyzed using the same method as for the primary efficacy endpoint.

The changes from baseline in CD4 cell count and CD4% at Weeks 48 and 96 will be summarized by treatment using descriptive statistics. The differences in changes from baseline in CD4 cell count and CD4% between 2 treatment groups and the associated 95% confidence intervals will be constructed using ANOVA models, including treatment (B/F/TAF vs. DTG + F/TDF) and baseline HIV-1 RNA (\leq 100,000 copies/mL vs. > 100,000 copies/mL) as fixed effects in the model.

In addition, missing CD4 cell count will be imputed using Last Observation Carried Forward (LOCF) method and analyzed similarly.

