To control type I error for the assessment of the primary and the co-primary efficacy endpoints, the hypothesis testing will be performed using the fallback procedure {[Wiens 2005](#)} in the sequential order with pre-specified 1-sided alpha level. The primary hypothesis of noninferiority of B/F/TAF relative to DTG + F/TDF, with respect to the proportion of subjects with HIV-1 RNA < 50 copies/mL at Week 48 (as defined by the FDA snapshot analysis) will be tested first. Non-inferiority test will be performed at one-sided, 0.025 alpha level. If non-inferiority is established, the co-primary hypothesis of noninferiority of B/F/TAF relative to DTG + F/TDF, with respect to the proportion of subjects with plasma HBV DNA < 29 IU/mL at Week 48 using Missing = Failure approach will be tested second at one-sided, 0.025 alpha level. Otherwise, the co-primary endpoint will not be tested at all.

The secondary anti-HIV efficacy endpoints include:

- 1) the proportion of subjects with HIV-1 RNA < 50 copies/mL at Week 96 as defined by the US FDA-defined snapshot algorithm, which will be analyzed in a similar manner as described for the primary efficacy endpoint.

- 2) the change from baseline in CD4 and CD4% at Weeks 48 and 96, which will be summarized by treatment using descriptive statistics. The differences and the associated 2-sided 95% CIs will be constructed using an Analysis of Variance (ANOVA) model, including treatment (B/F/TAF vs. DTG + F/TDF), HIV-1 RNA ($\leq 100,000$ copies/mL vs. $> 100,000$ copies/mL) as fixed effects in the model.

The secondary anti-HBV efficacy endpoints include:

- 1) the proportion of subjects with plasma HBV DNA < 29 IU/mL at Week 96
- 2) the proportion of subjects with ALT normalization at Weeks 48 and 96
- 3) the proportion of subjects with HBsAg loss at Weeks 48 and 96.

Each of these secondary anti-HBV efficacy endpoints will be analyzed in the same manner as described for the primary efficacy endpoint, except that stratification factors for the secondary efficacy endpoints include HBeAg status (positive vs. negative) and baseline HBV DNA ($< 8 \log_{10}$ IU/mL vs. $\geq 8 \log_{10}$ IU/mL).

The adverse events and clinical laboratory data will be summarized using descriptive statistics.

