1.2.3.3. Summary of Phase 2 Study (GS-US-141-1475)

Study GS-US-141-1475 is an ongoing Phase 2, randomized, double-blind, multicenter, active-controlled study to assess the safety and efficacy of a regimen containing B+F/TAF versus dolutegravir (DTG)+F/TAF in HIV-infected, ART-naïve adult subjects.

Eligible subjects were randomized in a 2:1 ratio to one of the following treatment groups, stratified by HIV-1 RNA level ($\leq 100,000$ copies/mL, $> 100,000$ copies/mL to $\leq 400,000$ copies/mL, or $> 400,000$ copies/mL) at screening:

- Treatment Group 1: Bicitegravir 75 mg + F/TAF (200/25 mg) + placebo-to-match DTG 50 mg once daily
- Treatment Group 2: DTG 50 mg + F/TAF (200/25 mg) + placebo-to-match bicitegravir 75 mg once daily

Week 48 interim data are summarized below.

Subject Disposition and Baseline Characteristics

A total of 98 subjects were randomized and treated in the study: 65 subjects in the B+F/TAF group and 33 subjects in the DTG+F/TAF group. At the time of the Week 48 data analysis, 5 subjects (5.1%) had prematurely discontinued study drug, 3 in the B+F/TAF group and 2 in the DTG+F/TAF group. The reasons for study drug discontinuation were as follows (one subject each): AE, withdrawal of consent, and lost to follow-up in the B+F/TAF group, and noncompliance with study drug and lost to follow up in the DTG+F/TAF group.

Demographic and baseline characteristics were similar between the 2 treatment groups. Key baseline disease characteristics (ie, viral load, CD4+ cell count, and estimated glomerular filtration rate [eGFR]_{CG}) were similar between the 2 treatment groups.

Median (Q1, Q3) baseline HIV-1 RNA was 4.45 (3.96, 4.79) log₁₀ copies/mL, with 82.7% having ≤ 100,000 copies/mL at baseline. Five subjects (5.1%) had > 400,000 copies/mL at baseline; of these, 4 subjects were randomized to B+F/TAF and 1 subject was randomized to DTG+F/TAF.

Median (Q1, Q3) baseline CD4+ cell count was 444 (316, 595) cells/μL, with 41.8% of subjects having ≥ 500 cells/μL at baseline. Median (Q1, Q3) baseline eGFR_{CG} was 125.3 (105.7, 147.0) mL/min.

Efficacy Results

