The primary efficacy endpoint was the proportion of subjects with HIV-1 RNA < 50 copies/mL at Week 24 as determined by the United States (US) Food and Drug Administration (FDA)-defined snapshot algorithm. The percentages of subjects with HIV-1 RNA < 50 copies/mL at Week 24 was high in both groups, as follows: BIC+F/TAF 96.9%; DTG+F/TAF 93.9%; difference in percentages: 2.9%, 95% CI: -8.5% to 14.2%. Because the lower bound of the 95% CI for the difference in response rate (B+F/TAF – DTG+F/TAF) was greater than the prespecified -12% margin, B+F/TAF was determined to be noninferior to DTG+F/TAF.

The percentages of subjects with HIV-1 RNA < 50 copies/mL at Week 48 were similar between the 2 treatment groups when assessed using the US FDA-defined snapshot algorithm based on the full analysis set (FAS) (Table 1-5), as follows: B+F/TAF 96.9%; DTG+F/TAF 90.9%; difference in percentages: 6.4%, 95% CI: -6.0% to 18.8%.

As expected for an INSTI-containing regimen, HIV-1 RNA levels decreased rapidly in the first 4 weeks following initiation of study drug in both treatment groups. After Week 4, HIV-1 RNA values were stable and similar between the 2 treatment groups through Week 48; mean (SD) decreases from baseline at Week 48 using the FAS were as follows: B+F/TAF -3.09 (0.752) log₁₀copies/mL; DTG+F/TAF -3.11 (0.852) log₁₀copies/mL; difference in least-squares mean (LSM): -0.06 log₁₀copies/mL, 95% CI: -0.32 to 0.20 log₁₀ copies/mL.

The mean (SD) increases from baseline in CD4+ cell counts were similar between the 2 treatment groups through Week 48 using the FAS, as follows: B+F/TAF 258 (221.7) cells/ μ L; DTG+F/TAF 192 (242.0) cells/ μ L; difference in LSM: 72 cells/ μ L, 95% CI: -30 to 174 cells/ μ L.

Table 1-5. GS-US-141-1475: Virologic Outcome at Week 48 Using the US FDA-Defined Snapshot Algorithm and HIV-1 RNA < 50 copies/mL (FAS)

	B+F/TAF (N = 65)	DTG+F/TAF (N = 33)	B+F/TAF vs DTG+F/TAF	
			p-value ^a	Difference in Percentages (95% CI) ^b
HIV-1 RNA < 50 copies/mL	63 (96.9%)	30 (90.9%)	0.17	6.4% (-6.0% to 18.8%)
HIV-1 RNA \geq 50 copies/mL	1 (1.5%)	2 (6.1%)		
HIV-1 RNA \geq 50 copies/mL in Week 48 window	0	1 (3.0%)		
Discontinued study drug due to lack of efficacy	0	0		
Discontinued study drug due to other reasons and last available HIV-1 RNA \geq 50 copies/mL ^c	1 (1.5%)	1 (3.0%)		
No virologic data in Week 48 window	1 (1.5%)	1 (3.0%)		
Discontinued study drug due to AE/death	1 (1.5%)	0		

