3.3. Study Treatments

Subjects who provide written consent and meet all eligibility criteria will be randomized in a 1:1 ratio to one of the following two treatment groups:

[figure not shown]
Treatment Group 1 (n=120): FDC of bicitegravir 50 mg/emtricitabine 200 mg/ tenofovir alafenamide 25 mg (B/F/TAF) + placebo to match dolutegravir 50 mg (DTG) and placebo to match FDC of emtricitabine 200 mg/tenofovir disoproxil fumarate 300 mg (F/TDF) administered orally, once daily, without regard to food

Treatment Group 2 (n=120): dolutegravir 50 mg (DTG) + FDC of emtricitabine 200 mg/ tenofovir disoproxil fumarate 300 mg (F/TDF) + Placebo to match FDC of bicitegravir 50 mg/emtricitabine 200 mg/ tenofovir alafenamide 25 mg (B/F/TAF) administered orally, once daily, without regard to food

Randomization will be stratified by HBeAg (positive vs. negative), HBV DNA (< 8 log₁₀ IU/mL vs. ≥ 8 log₁₀ IU/mL), CD4⁺ cell count (< 50 cells/μL vs. ≥ 50 cells/μL) at Screening.

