- h. Chemistry profile: alkaline phosphatase, AST, ALT, GGT, total bilirubin, direct and indirect bilirubin, total protein, albumin, bicarbonate, BUN, calcium, chloride, creatinine, glucose, phosphorus, magnesium, potassium, sodium, uric acid and amylase (reflex lipase testing is performed in subjects with total amylase $> 1.5 \times$ ULN). At Day 1, Weeks 24, 48, 72, 96, every 24 weeks post Week 96, and End of Blinded Treatment Visit, analyses of glucose will be done as part of the fasting metabolic assessments every 24 weeks and not as part of the chemistry profile. PT/INR will be performed at Screening and Day 1.

- i. Fasting (no food or drinks, except water, at least 8 hours prior to blood collection) glucose and lipid panel (total cholesterol, HDL, direct LDL, triglycerides). If the subject has not fasted prior to the visit, the visit may proceed, but the subject must return within 72 hours in a fasted state to draw blood for the metabolic assessments. After Week 96 Visit, metabolic assessments will be completed every 24 weeks.
- j. Complete blood count with differential and platelet count.
- k. The Investigator must have received the results from the screening HIV-1 genotype report before proceeding with the Day 1 visit. Screening HIV-1 genotype report must show sensitivity to TFV and FTC. If genotype results from a local laboratory obtained ≤ 90 days prior to screening visit date show sensitivity to these drugs, this genotype will be acceptable to fulfill this inclusion criterion in the event that the genotype obtained at screening is not yet available and all other inclusion/exclusion criteria have been confirmed.
- l. Trough PK blood sample will be obtained 20-28 hours following the last dose at Weeks 4, 12 and 36.
- m. Following an observed dose, one post-dose PK blood sample will be collected between 1 and 4 hours post-dose at Weeks 8 and 24.
- n. CD4+ cell count and CD4% to be completed at all study visits.
- o. Plasma and serum blood storage samples will be collected for safety, virology or PK testing. Whole blood storage samples will be collected for safety, virology or PK testing at Day 1, Week 48 and Week 96 visits.

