If the last dose date for the all B/F/TAF analysis is missing (eg, only year of last dose date is known or completely missing due to lost to follow-up), the latest of the B/F/TAF (including both phases) start dates and end dates, the latest clinical and laboratory visit dates, excluding the 30-day follow-up visit date, will be used to impute the last dose date.

Study Days are calculated relative to Study Day 1 for either the randomized phase analysis or the all B/F/TAF analysis, as appropriate. For events that occurred on or after the Study Day 1 date of either analysis, study days are calculated as (visit date minus the date of Study Day 1 plus 1). For events that occurred prior to Study Day 1 for either analysis, study days are calculated as visit date minus the date of Study Day 1.

Last Study Date is the latest of the study drug (including B/F/TAF and DTG + F/TDF in both phases) start dates and end dates, the clinic visit dates, and the laboratory visit dates, including the 30-day follow-up visit date.

Baseline Value is defined as the last nonmissing value obtained on or prior to Study Day 1 for either the randomized phase analysis or the all B/F/TAF analysis, as appropriate. Participants who actually received DTG + F/TDF in the randomized phase and received at least 1 dose of B/F/TAF in extension phase will have a new baseline value for the All B/F/TAF analysis.

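### The planned CD4 comparison leaves out the baseline CD4 value already collected; it is valid, but less precise than ANCOVA unless follow-up CD4 tracks baseline about one-for-one

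*Protocol*

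**What the plan says.** Protocol 8.5.2.1 estimates the between-arm difference in change from baseline in CD4 count and CD4%, with 95% intervals, "constructed using ANOVA models, including treatment (B/F/TAF vs. DTG + F/TDF) and baseline HIV-1 RNA" (at most versus above 100,000 copies/mL). The synopsis gives the same model: "constructed using an Analysis of Variance (ANOVA) model, including treatment (B/F/TAF vs. DTG + F/TDF), HIV-1 RNA" category. A further analysis follows the same form: "missing CD4 cell count will be imputed using Last Observation Carried Forward (LOCF) method and analyzed similarly". None of these includes baseline CD4 count or CD4%.

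The baseline values are there to use. Appendix 2 schedules both measures at Screening and Day 1, and its footnote n reads "CD4+ cell count and CD4% to be completed at all study visits". SAP 3.8.1 supplies the definition: "Baseline Value is defined as the last nonmissing value obtained on or prior to Study Day 1".

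Protocol 3.3 says "Randomization will be stratified by HBeAg (positive vs. negative), HBV DNA" and screening CD4 count, the last only as below 50 versus 50 or more cells/µL. That CD4 stratum is not in the CD4 model either.

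The supplied SAP covers the final analysis. Its Section 6.3.2.2 summarises CD4 change descriptively with no between-arm comparison. Section 6.2.1.2 refers the Week 48 and Week 96 secondary methods to earlier SAPs, which were not supplied.

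**The concern.** Subtracting baseline is not the same as adjusting for it. Change from baseline fixes the coefficient of baseline CD4 at 1. If the true slope of follow-up on baseline differs from 1, part of the baseline variation stays in the change score and widens the interval. In any one trial, the same mechanism leaves a fraction (slope minus 1) of the chance baseline difference between arms in the estimated treatment difference. With a slope below 1, the arm that happens to start higher looks worse.

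Stratified randomization offers little protection. A cut at 50 cells/µL does not balance CD4 above 50. For scale, the lower quartile in the Phase 2 study (Protocol 1.2.3.3) was 316, so at least three quarters of those subjects sat well above the cut.

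What is at stake is the precision and readability of a secondary result. Validity and the primary conclusions are not in question.

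**Working it through.** The documents give no SD, power or slope for the CD4 comparison in this trial, so there is no planned figure to reproduce. The inputs below come from the Phase 2 study in Protocol 1.2.3.3 and serve only as illustration.

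**Inputs**
- SD of Week 48 CD4 change: 221.7 (65 subjects in the arm) and 242.0 (33 subjects).
- Baseline CD4 quartiles: 316 and 595.
- Planned size: 120 per arm (Protocol 8.8).
- Slope *b* of follow-up on baseline CD4: not given; assumed 0.5 to 1.2.

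**Spread**
- Pooled change SD = √[(64 × 221.7² + 32 × 242.0²)/96] = 228.7.
- Baseline SD ≈ (595 − 316)/1.349 = 206.8, assuming rough normality.

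**Check against the Phase 2 interval.** The reported interval of −30 to 174 has half-width (174 + 30)/2 = 102. The pooled SD gives 1.985 × 228.7 × √(1/65 + 1/33) = 97.0, which is broadly consistent. Working back from 102 implies an SD of about 240, if all 98 subjects contributed.

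**Planned ANOVA at 120 per arm.** Half-width = 1.96 × 228.7 × √(2/120) = 57.9 cells/µL. It is about 61 with the implied SD of 240, and 57.5 with the 243 treated subjects in SAP Appendix 3.

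**ANCOVA against ANOVA.** Var(change) = residual variance + (*b* − 1)² × Var(baseline), and ANCOVA leaves only the residual variance. The variance ratio is therefore 1 − (1 − *b*)² × 206.8²/228.7². The ANOVA interval is wider by 1/√ratio − 1.

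**Carry-over of imbalance.** The SD of the chance baseline difference between arms is 206.8 × √(2/120) = 26.7 cells/µL. If B/F/TAF starts one such SD higher, the ANOVA difference shifts by (*b* − 1) × 26.7.

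| Assumed slope | Variance ratio | ANCOVA half-width | ANOVA wider by | Same, baseline SD 150 to 250 | Shift (cells/µL) |
|---|---|---|---|---|---|
| 1.2 | 0.967 | 56.9 | 1.7% | 0.9% to 2.5% | +5.3 |
| 1.0 | 1.000 | 57.9 | 0% | 0% | 0 |
| 0.8 | 0.967 | 56.9 | 1.7% | 0.9% to 2.5% | −5.3 |
| 0.6 | 0.869 | 53.9 | 7.3% | 3.6% to 11.2% | −10.7 |
| 0.5 | 0.795 | 51.6 | 12.1% | 5.9% to 19.4% | −13.4 |

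**Simulation.** With 4,000 trials of 240 subjects per slope and a true difference of zero:
- The mean ANOVA estimate was within 0.6 cells of zero, with coverage of 94.8% to 95.1%.
- Mean half-widths were 58.2 to 58.3 for ANOVA, against 57.5, 58.3, 57.4, 54.4 and 52.0 for ANCOVA at slopes 1.2, 1.0, 0.8, 0.6 and 0.5.
- The regression of the ANOVA estimate on baseline imbalance was +0.18, 0.01, −0.20, −0.41 and −0.49 at those slopes. For ANCOVA it stayed between −0.01 and 0.01.

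A separate simulation kept a two-level stratum in both models (3,000 trials per slope, outcome in residual-SD units). Both models were unbiased. The empirical standard errors, ANOVA against ANCOVA, were 0.148 against 0.132 at slope 0.5, 0.133 against 0.127 at 0.7, and equal at 0.9 to 1.1.

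For CD4% the documents give no SD, so no figure can be put on it.

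**The case against.** The strongest reply is that nothing here is an error. The ANOVA is unbiased, its interval covers as it should, and the Protocol promises only summaries, a difference and a 95% interval. That stands: the point concerns efficiency.

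The size is also not established. No document gives the slope, and between 0.8 and 1.2 the loss is at most about 2%. The spreads come from 98 HIV-infected subjects not selected for HBV, and CD4 in this trial may be distributed differently. The variance ratio also ignores the HIV-1 RNA category already in the model. If that category explains some baseline CD4 variation, the added gain is somewhat smaller. All of this stands, and is why the figures are illustrations and not bounds.

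The shift from chance imbalance is the source of the extra variance, not a second harm. The valid interval already allows for it. Even the 13-cell shift at slope 0.5 is under a quarter of the 58-cell half-width.

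Finally, the Week 48 and Week 96 SAPs may already contain the term, and those analyses are finished. This limits what can be done, but it does not remove the point about the Protocol text. The final SAP (Section 6.4) reports no planned change from the Protocol's efficacy analysis, which gives no sign that the term was added, though it does not settle what the earlier SAPs say.

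None of this favours leaving the covariate out. At a slope of 1 it costs one degree of freedom in about 240 subjects; away from 1 it narrows the interval.

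**Conclusion.** The concern holds for the Protocol. The planned CD4 model is valid but omits an available covariate, and it loses precision unless the slope of follow-up on baseline is near 1. On borrowed Phase 2 spreads the loss runs from nothing at slope 1.0 to about 12% of interval width at 0.5, or 6% to 19% at 0.5 if the baseline SD lies between 150 and 250. It is negligible for slopes of about 0.9 to 1.1. These figures rest on an assumed slope, a normal approximation for the baseline SD, and the transfer of Phase 2 inputs to a co-infected population. The endpoint is secondary, with no margin and no alpha, so no primary conclusion changes. Whether the completed analyses were affected cannot be told from the documents supplied.

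**What to change.** The model in Protocol 8.5.2.1 and the synopsis should carry continuous baseline CD4 count (baseline CD4% for the CD4% endpoint) alongside treatment and HIV-1 RNA category. This applies to the observed CD4 count and CD4% analyses and to the LOCF CD4 count analysis.

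SAP 2.2.1, 2.2.2 and 6 state that the Week 48 and Week 96 analyses are done, so the first step is to read their SAPs. If the term is there, nothing more is needed. If it is not, keep the planned ANOVA as the prespecified result and report the ANCOVA beside it as a supplementary analysis, clearly labelled post hoc.

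The cost is one supplementary table and one degree of freedom per model, with no new data.
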